## Appendix 2 Clinical Laboratory Tests

Pregnancy test: Blood or Urine Human chorionic gonadotropin (hCG)
 
Hematology: Hemoglobin Platelet count White blood cell count Absolute neutrophils, lymphocytes, and eosinophils
 
Serum chemistry: Albumin Alkaline phosphatase Alanine aminotransferase Amylase Aspartate aminotransferase Bicarbonate Bilirubin (Total and Direct) Blood urea nitrogen Calcium Chloride Creatinine Glucose Lipase Magnesium Phosphate Potassium Sodium Urate
	
Coagulation: Prothrombin time (PT) Activated Partial Thromboplastin Time (aPTT) INR Fibrinogen
 
Endocrine tests: Free thyroxine Thyroid-stimulating hormone
 
Urinalysis: Protein Occult blood

--	---

### **Appendix 3      Pharmacokinetics, Immunogenicity, and Pharmacodynamic Biomarkers Blood Sampling Schedule for MGD007 & MGA012**

Blood samples for MGD007 and MGA012 PK, ADA, and PD biomarkers will be collected per [Table 15](#).

**Table 15 Pharmacokinetic, Immunogenicity, and Pharmacodynamic Biomarkers Blood Sampling Schedule for MGD007 & MGA012 **

Cycle	Day	MGD007 & MGA012 PK Sampling Time 	MGD007 & MGA012 ADA Sampling Time	Cytokines 	Flow Cytometry Occupancy	Flow Cytometry Subsets	Serum Bio-markers 	T-cell repertoire 	ctDNA analysis 	Transcript profile 
1	1	Pre MGD007 infusion	Pre MGD007 infusion	Pre MGD007 infusion	Pre MGD007 infusion	Pre MGD007 infusion	Pre MGD007 infusion	Pre MGD007 infusion	Pre MGD007 infusion	Pre MGD007 infusion
	1	End of MGD007 infusion								
	1	2 hours after end of MGD007 infusion		2 hours after end of MGD007 infusion	2 hours after end of MGD007 infusion	2 hours after end of MGD007 infusion				
	1	6 hours after end of MGD007 infusion		6 hours after end of MGD007 infusion						
1	2			Day 2	Day 2	Day 2				
1	8	Pre MGD007 infusion			Pre MGD007 infusion	Pre MGD007 infusion	Pre MGD007 infusion			
	8	End of MGD007 infusion								
	8				2 hours after end of MGD007 infusion	2 hours after end of MGD007 infusion				
1	15	Pre MGA012 infusion	Pre MGA012 infusion	Pre MGA012 infusion	Pre MGA012 infusion	Pre MGA012 infusion	Pre MGA012 infusion			

**Table 15 Pharmacokinetic, Immunogenicity, and Pharmacodynamic Biomarkers Blood Sampling Schedule for MGD007 & MGA012 **

Cycle	Day	MGD007 & MGA012 PK Sampling Time 	MGD007 & MGA012 ADA Sampling Time	Cytokines 	Flow Cytometry Occupancy	Flow Cytometry Subsets	Serum Bio-markers 	T-cell repertoire 	ctDNA analysis 	Transcript profile 
1	15	End of MGA012 infusion								
	15	End of MGD007 infusion								
	15				2 hours after end of MGD007 infusion	2 hours after end of MGD007 infusion				
	15	1 hour after end of MGD007 infusion								
	15	2 hours after end of MGD007 infusion								
	15	4 hours after end of MGD007 infusion								
	15			6 hours after end of MGD007 infusion						
1	16	Day 16		Day 16	Day 16	Day 16				
1	17	Day 17								
1	19	Day 19								

**Table 15 Pharmacokinetic, Immunogenicity, and Pharmacodynamic Biomarkers Blood Sampling Schedule for MGD007 & MGA012 **

Cycle	Day	MGD007 & MGA012 PK Sampling Time 	MGD007 & MGA012 ADA Sampling Time	Cytokines 	Flow Cytometry Occupancy	Flow Cytometry Subsets	Serum Bio-markers 	T-cell repertoire 	ctDNA analysis 	Transcript profile 
1	22	Pre MGD007 infusion				Pre MGD007 infusion				
	22	End of MGD007 infusion				End of MGD007 infusion				
1	29	Pre MGA012 infusion	Pre MGA012 infusion	Pre MGA012 infusion	Pre MGA012 infusion	Pre MGA012 infusion	Pre MGA012 infusion			
	29	End of MGA012 infusion								
	29	End of MGD007 infusion			End of MGD007 infusion	End of MGD007 infusion				
	29			2 hours after end of MGD007 infusion						
1	42							Pre Biopsy	Pre Biopsy	Pre Biopsy
1	43	Pre MGA012 infusion								
	43	End of MGA012 infusion								
	43	End of MGD007 infusion								

**Table 15 Pharmacokinetic, Immunogenicity, and Pharmacodynamic Biomarkers Blood Sampling Schedule for MGD007 & MGA012 **

Cycle	Day	MGD007 & MGA012 PK Sampling Time 	MGD007 & MGA012 ADA Sampling Time	Cytokines 	Flow Cytometry Occupancy	Flow Cytometry Subsets	Serum Bio-markers 	T-cell repertoire 	ctDNA analysis 	Transcript profile 
2	1	Pre MGA012 infusion	Pre MGA012 infusion	Pre MGA012 infusion	Pre MGA012 infusion	Pre MGA012 infusion	Pre MGA012 infusion	Pre MGA012 infusion	Pre MGA012 infusion	
	1	End of MGA012 infusion								
	1	End of MGD007 infusion			End of MGD007 infusion					
	1			2 hours after end of MGD007 infusion						
2	2			Day 2						
2	15	Pre MGA012 infusion								
	15	End of MGA012 infusion								
	15	End of MGD007 infusion								
2	29				Pre MGA012 infusion	Pre MGA012 infusion				
	29				End of MGD007 infusion					

**Table 15 Pharmacokinetic, Immunogenicity, and Pharmacodynamic Biomarkers Blood Sampling Schedule for MGD007 & MGA012 **

Cycle	Day	MGD007 & MGA012 PK Sampling Time 	MGD007 & MGA012 ADA Sampling Time	Cytokines 	Flow Cytometry Occupancy	Flow Cytometry Subsets	Serum Bio-markers 	T-cell repertoire 	ctDNA analysis 	Transcript profile 
3	1	Pre MGA012 infusion	Pre MGA012 infusion			Pre MGA012 infusion	Pre MGA012 infusion	Pre MGA012 infusion	Pre MGA012 infusion	
	1	End of MGA012 infusion								
	1	End of MGD007 infusion								
3	29					Pre MGA012 infusion				
4	1	Pre MGA012 infusion	Pre MGA012 infusion			Pre MGA012 infusion	Pre MGA012 infusion			
	1	End of MGA012 infusion								
	1	End of MGD007 infusion								
4	29					Pre MGA012 infusion				
5 and Subsequent Cycles	1	Pre MGA012 infusion	Pre MGA012 infusion							

**Table 15 Pharmacokinetic, Immunogenicity, and Pharmacodynamic Biomarkers Blood Sampling Schedule for MGD007 & MGA012 **

Cycle	Day	MGD007 & MGA012 PK Sampling Time 	MGD007 & MGA012 ADA Sampling Time	Cytokines 	Flow Cytometry Occupancy	Flow Cytometry Subsets	Serum Bio-markers 	T-cell repertoire 	ctDNA analysis 	Transcript profile 
5 and Subsequent Cycles	1	End of MGA012 infusion								
	1	End of MGD007 infusion								
EOT Visit		EOT	EOT		EOT	EOT				
		IRR/CRS		IRR/CRS						

Note: Do not collect PK samples from infusion port; samples will be collected from the contralateral arm. When collecting multiple samples, collect the PK sample first. Actual start and end of infusion times and all sample collection times will be recorded on the CRFs. All sample time points are hours (h) after EOI, unless otherwise specified.

Note: Duration of infusion for MGA012 = 60 minutes and for MGD007 = 120 minutes

- 1 Window times for samples required at EOI or after EOI are as follows: up to -10 minutes before the infusion is complete; ± 10 min for samples to be collected at 1, 2, 4, 6 hours after EOI.
- 2 Additional samples may be obtained selectively at additional time points in patients who experience signs and symptoms of cytokine release.
- 3 Cohort Expansion Subjects only. Samples on Cycle 1 Day 42 are for subjects having biopsies only.

Abbreviations: ADA = Anti-drug antibody; EOI = End of infusion; EOT = End of treatment; PK = Pharmacokinetic; QW = Once a week; Trt = Treatment

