## **10 ASSESSMENT OF PHARMACOKINETICS AND PHARMACODYNAMICS**

### **10.1 Pharmacokinetics Assessments**

Serum concentrations of study drug will be monitored using a quantitative sandwich enzyme-linked immunosorbent assay (ELISA) method in the Sponsor's designated central laboratory. Single and multiple dose PK parameters, maximal concentration ( $C_{max}$ ), time to maximal concentration ( $T_{max}$ ), area under the concentration-time curve from time zero to time T ( $AUC_{(0-T)}$ ), area under the concentration-time curve in a dosing interval ( $AUC_{tau}$ ), area under the concentration-time curve from time zero to infinite time ( $AUC_{(INF)}$ ), trough concentration ( $C_{trough}$ ), clearance (CL), volume of distribution at steady state ( $V_{ss}$ ), and terminal half-life ( $t_{1/2}$ ), will be derived from serum concentration versus time data. Population PK analyses may be conducted using data from this study alone or combined with data from other studies.

Analysis of PK data will be carried out using industry standard software. Population PK modeling may be performed, and an appropriate model and model parameters may be described. Samples will be collected for evaluation of ADA.

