  - 3 Post-treatment follow-up collected every 3 months by phone or other electronic contact; response status, if available, will be collected every 3 months in patients who discontinued from study treatment due to reasons other than progressive disease, if they have not initiated any other cancer-directed therapy. See [Section 9.12](#).
  - 4 See [Appendix 3](#) for samples to be collected at visit.
- Abbreviations: CEA = carcinoembryonic antigen; D = day; ECG = Electrocardiogram; EOI = end of infusion; EOTV = end of treatment visit;

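### First-dose MGD007 has no PK sample between 6 hours after end of infusion and Day 8, although blood is drawn on Cycle 1 Day 2; noncompartmental first-dose AUC could be materially overstated

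*Protocol*

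**What the plan says.** Table 15 in Protocol Appendix 3 schedules Cycle 1 Day 1 PK before the infusion, at end of infusion, at 2 hours after it, and "6 hours after end of MGD007 infusion". The next PK entry is Day 8, "Pre MGD007 infusion". The Day 2 row has entries for cytokines, flow cytometry occupancy and flow cytometry subsets, and an empty PK cell. Day 2 is a planned visit: footnote 4 to the Appendix 1 schedule refers to Appendix 3 "for samples to be collected at visit".

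The dose given with the first MGA012 infusion is followed much more closely. Day 15 has PK samples up to "4 hours after end of MGD007 infusion", then on Days 16, 17 and 19 and before the Day 22 infusion. The Day 16 row has the same three draws as Day 2, plus PK.

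Protocol 10.1 plans "Single and multiple dose PK parameters", including AUC, CL, Vss and half-life. Neither Protocol 10.1 and 14.5.1 nor SAP 6.8 says how they will be estimated, and population PK is optional. Footnote 2 to Table 15 allows extra PK samples, but only for some patients: "Additional samples may be obtained selectively at additional time points in patients who experience signs and symptoms of cytokine release".

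**The concern.** The first dose is the only one given with no earlier study drug in the patient. The second MGD007-alone week is sampled only before and at the end of the Day 8 infusion and before dosing on Day 15. No mid-interval MGD007 concentration is therefore scheduled before MGA012 starts.

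Pharmacokinetics is a secondary objective in both phases (Protocol 3.1.2 and 3.2.2). If the single-dose parameters come from a trapezoid rule, one straight or log-straight segment stands in for almost the whole dosing interval. A curve with a distribution phase lies below that segment, so AUC is overstated, and CL calculated as dose over AUC(INF) is understated. Also, the Day 2 cytokine and receptor-occupancy results have no concentration from the same draw, although Protocol 14.5.3 allows pharmacodynamic changes to be related to exposure.

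**Working it through.** **Inputs from the documents.** Table 4 overall means: CL 1.09 mL/h/kg, Vss 70.72 mL/kg, half-life 55.42 h. Table 5, first dose at 0.4 µg/kg: Cmax 10.04 ng/mL, AUC(TAU) 344.91 ng·h/mL, Ctrough 0.36 ng/mL. Infusion time, from the Table 15 notes: "Duration of infusion for MGA012 = 60 minutes and for MGD007 = 120 minutes".

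**Assumed.** V1 38 mL/kg; terminal half-life 46-80 h; noise-free profiles at nominal times. Arithmetic means (Table 4) are combined with geometric means (Table 5).

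**The plan's own figure.** Scaling the 1 µg/kg value gives 0.4 × 862.27 = 344.91, as stated. A one-compartment model with CL 1.09 and V 70.72 gives AUC(TAU) 339.0 (-1.7%) but Cmax (200/1.09) × (1 - e^(-2 × 1.09/70.72)) = 5.6, against 10.04 in Table 5. The documents' figures therefore point to a distribution phase.

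**The gap.** Six hours after a 2 h infusion is 8 h from start; Day 8 pre-dose is 168 h. The gap is 160 h: 160/168 = 95% of the interval and 160/55.42 = 2.9 mean half-lives. With the ±1 day window on Day 8 it runs from 136 to 184 h.

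**Model.** Dose 400 ng/kg, R = 200 ng/kg/h, T = 2 h, V2 = 70.72 - 38 = 32.72. With k10 = CL/V1, k12 = Q/V1, k21 = Q/V2, α and β are the roots of s² - (k10 + k12 + k21)s + k10·k21 = 0, and Q is solved so that ln 2/β equals the assumed half-life. After the infusion, C(t) = (R/V1)·[(α - k21)/(α - β)·(1 - e^(-αT))/α·e^(-α(t-T)) + (k21 - β)/(α - β)·(1 - e^(-βT))/β·e^(-β(t-T))].

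**One case in full, half-life 55 h.** C(8) = 7.05, C(26) = 3.42, C(168) = 0.444 ng/mL; true AUC(TAU) 331.8, of which 60.4 lies before 8 h.
- As scheduled, log-down: 160 × (7.05 - 0.444)/ln(7.05/0.444) = 382; 382 + 60 = 442, or +33%.
- As scheduled, linear: 160 × (7.05 + 0.444)/2 = 600; 600 + 60 = 660, or +99%.
- With Day 2 at 26 h (24 h after end of infusion), log-down: 18 × (7.05 - 3.42)/ln(7.05/3.42) + 142 × (3.42 - 0.444)/ln(3.42/0.444) = 90 + 207; plus 60 gives 357, or +8%. Linear gives 429, or +29%.

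**Range** (sampling at 0, 2, 4, 8 and 168 h, without and with 26 h):

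| Terminal half-life (h) | Cmax (ng/mL) | AUC(TAU) in gap | Log-down: planned → with Day 2 | Linear: planned → with Day 2 |
|---|---|---|---|---|
| 46 | 8.3 | 87% | +1% → 0% | +40% → +23% |
| 48 | 9.4 | 84% | +13% → +2% | +60% → +22% |
| 50 | 9.7 | 83% | +22% → +3% | +77% → +23% |
| 55 | 9.9 | 82% | +33% → +8% | +99% → +29% |
| 70 | 10.1 | 81% | +40% → +16% | +119% → +44% |
| 80 | 10.1 | 80% | +38% → +17% | +123% → +49% |

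**Half-life from the last three points.** It moves from 39.0 to 42.9 h when the true value is 55 h, and from 35.0 to 37.1 h when it is 80 h. One Day 2 sample barely helps.

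**Other disposition assumptions.** Two-compartment fits to Table 5 with terminal half-life 55-90 h give planned AUC(TAU) errors of +31 to +34% (log-down) and +109 to +115% (linear). In those fits AUC(INF) by log-down is +23 to +26%, so CL would be about 19-21% low (1/1.23 = 0.81; 1/1.26 = 0.79). Very fast distribution with a half-life near 40 h gives -0.1% and +48%. Pure one-compartment decline gives 0% by log-down.

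**The case against.** The strongest reply is that the bias depends on a choice the documents leave open. The earlier MGD007 study fitted one- or two-compartment models to first-dose data (Protocol 2.6.1.1), and a well-specified fit here would be less affected than a trapezoid rule. Shorter half-lives are also plausible: Table 4 reports means of 37.61 and 39.02 h in the two 1 µg/kg groups (7 of 16 patients), and CL with Vss alone implies 0.693 × 70.72/1.09 = 45 h. Both points stand, which is why the log-down range starts near zero. The low-error cases fit the predicted Cmax less well, however (8.3 at 46 h, against 10.04).

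The intensive profile sits at Day 15, when the combination starts. That matches the objective of describing PK in combination, and it can support AUC(TAU) and half-life at that dose. This stands too, but it leaves the first dose unsupported. In a dose-proportionality power model, a roughly constant percentage error would mostly shift the level, not the slope.

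A reader might infer two stronger things. One is that the gap makes first-dose AUC and half-life badly biased. The documents do not support that, because no estimation method is named. The other is that Day 1 versus Day 15 is the trial's only within-patient look at whether MGA012 changes MGD007 exposure. It is not. End-of-infusion samples are scheduled on Days 1 and 8 (MGD007 alone) and on Days 15, 22, 29 and 43; pre-dose samples on Days 8 and 15 precede MGA012, and those on Days 22, 29 and 43 follow it. Peak and trough can therefore be compared at matched times, and no section plans a Day 1 versus Day 15 AUC comparison.

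**Conclusion.** The gap is real, and it covers about 80-87% of first-dose AUC(TAU) under the assumed model. If noncompartmental methods are used, the overstatement is about 1-40% by log-down or 40-123% by linear trapezoid, with the upper part better supported by Table 5. The size rests on the assumed V1 of 38 mL/kg and terminal half-life of 46-80 h, and on profiles without assay noise. The assay's quantification limit is not given; if a trough near 0.36 ng/mL fell below it, the first-dose terminal phase could not be estimated at all.

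This is a cheap improvement to a secondary objective. It does not affect the dose-escalation decisions or the response endpoints.

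**What to change.** Add an MGD007 PK sample to the Cycle 1 Day 2 row of Table 15, at a nominal 24 hours after end of infusion, as the Day 16 row already does. MGA012 has not yet been given, so only the MGD007 assay is needed. The AUC(TAU) error then falls to about 0-17% (log-down) or 22-49% (linear).

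This one sample does not correct first-dose half-life, and it does not make the Day 1 and Day 15 profiles fully comparable: sampling as on Days 15-22 gives an error of about 2% (log-down) or 6% (linear) or less. Protocol 10.1 and 14.5.1 and SAP 6.8 should therefore name the estimation method, and state that first-dose half-life, CL and Vss come from a model that also uses the Day 15-22 data.

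The cost is one extra tube and one assay per patient at an existing draw, or about 52 samples at the planned enrolment, with no new visit.

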## **Appendix 4 Eastern Cooperative Oncology Group (ECOG) Performance Status**

Grade	Description
0	Fully active, able to carry on all pre-disease performance without restriction.
1	Restricted in physically strenuous activity, but ambulatory and able to carry out work of a light or sedentary nature (e.g., light house work or office work)
2	Ambulatory and capable of all self-care, but unable to carry out any work activities. Up and about more than 50% of waking hours.
3	Capable of only limited self-care, confined to bed or chair more than 50% of waking hours.
4	Completely disabled. Cannot carry-on any self-care. Totally confined to bed or chair.
5	Dead

## Appendix 5      RECIST 1.1 Guidelines

Adapted from Eisenhauer 2009 (11).

All patients will be required to have at least 1 measurable lesion to be considered as having measurable disease at baseline for the determination of eligibility for this study. Measurable lesions are defined below.

### 1      Measurability of Tumor at Baseline

#### 1.1      Definitions

At baseline, tumor lesions/lymph nodes will be categorized measurable or non-measurable as follows:

##### 1.1.1      Measurable

*Tumor lesions:* Must be accurately measured in at least one dimension (*longest* diameter in the plane of measurement is to be recorded) with a *minimum* size of:

- 10 mm by CT scan (CT scan slice thickness no greater than 5 mm).
- 10 mm caliper measurement by clinical exam (lesions which cannot be accurately measured with calipers should be recorded as nonmeasurable).
- 20 mm by chest X-ray.

*Malignant lymph nodes:* To be considered pathologically enlarged and measurable, a lymph node must be  $\geq 15$  mm in *short* axis when assessed by CT scan (CT scan slice thickness recommended to be no greater than 5 mm). At baseline and in follow-up, only the *short* axis will be measured and followed. See also notes below on ‘Baseline documentation of target and nontarget lesions’ for information on lymph node measurement.

##### 1.1.2      Nonmeasurable

All other lesions, including small lesions (longest diameter  $< 10$  mm or pathological lymph nodes with  $\geq 10$  to  $< 15$  mm short axis) as well as truly non-measurable lesions. Lesions considered truly nonmeasurable include leptomeningeal disease, ascites, pleural or pericardial effusion, inflammatory breast disease, lymphangitic involvement of skin or lung, abdominal masses/abdominal organomegaly identified by physical exam that is not measurable by reproducible imaging techniques.

### 1.1.3 Special Considerations Regarding Lesion Measurability

Bone lesions, cystic lesions, and lesions previously treated with local therapy require particular comment:

Bone lesions:

- Bone scan, PET scan or plain films are not considered adequate imaging techniques to measure bone lesions. However, these techniques can be used to confirm the presence or disappearance of bone lesions.
- Lytic bone lesions or mixed lytic-blastic lesions, *with identifiable soft tissue components*, that can be evaluated by cross sectional imaging techniques such as CT or MRI can be considered as measurable lesions if the *soft tissue component* meets the definition of measurability described above.
- Blastic bone lesions are nonmeasurable.

Cystic lesions:

- Lesions that meet the criteria for radiographically defined simple cysts should not be considered as malignant lesions (neither measurable nor nonmeasurable) since they are, by definition, simple cysts.
- ‘Cystic lesions’ thought to represent cystic metastases can be considered as measurable lesions, if they meet the definition of measurability described above. However, if noncystic lesions are present in the same patient, these are preferred for selection as target lesions.

Lesions with prior local treatment:

- Tumor lesions situated in a previously irradiated area, or in an area subjected to other locoregional therapy, are not considered measurable unless there has been demonstrated progression in the lesion prior to study enrollment.

## 1.2 Specifications by methods of measurements

### 1.2.1 Measurement of lesions

All measurements should be recorded in metric notation, using calipers if clinically assessed. All baseline evaluations should be performed as close as possible to the treatment start and never more than 4 weeks before the beginning of the treatment.

### 1.2.2 Method of assessment

The same method of assessment and the same technique should be used to characterize each identified and reported lesion at baseline and during follow-up. Imaging based evaluation should

always be done rather than clinical examination unless the lesions(s) being followed cannot be imaged but are assessable by clinical exam.

*Clinical lesions:* Clinical lesions will only be considered measurable when they are superficial and  $\geq 10$  mm diameter as assessed using calipers (e.g. skin nodules). For the case of skin lesions, documentation by color photography including a ruler to estimate the size of the lesion is suggested. As noted above, when lesions can be evaluated by both clinical exam and imaging, imaging evaluation should be undertaken since it is more objective and may also be reviewed at the end of the study.

*Chest X-ray:* Chest CT is preferred over chest X-ray, particularly when progression is an important endpoint, since CT is more sensitive than X-ray, particularly in identifying new lesions. However, lesions on chest X-ray may be considered measurable if they are clearly defined and surrounded by aerated lung.

*CT, MRI:* CT is the best currently available and reproducible method to measure lesions selected for response assessment. This guideline has defined measurability of lesions on CT scan based on the assumption that CT slice thickness is 5 mm or less. When CT scans have slice thickness greater than 5 mm, the minimum size for a measurable lesion should be twice the slice thickness. MRI is also acceptable in certain situations (e.g., for body scans).

*Ultrasound:* Ultrasound is not useful in assessment of lesion size and should not be used as a method of measurement. Ultrasound examinations cannot be reproduced in their entirety for independent review at a later date and, because they are operator dependent, it cannot be guaranteed that the same technique and measurements will be taken from one assessment to the next. If new lesions are identified by ultrasound in the course of the study, confirmation by CT or MRI is advised. If there is concern about radiation exposure at CT, MRI may be used instead of CT in selected instances.

*Endoscopy, laparoscopy:* The utilization of these techniques for objective tumor evaluation is not advised.

*Tumor markers:* Tumor markers *alone* cannot be used to assess *objective* tumor response.

## **2 Tumor Response Evaluation**

### **2.1 Assessment of Overall Tumor Burden and Measurable Disease**

To assess objective response or future progression, it is necessary to estimate the *overall tumor burden at baseline* and use this as a comparator for subsequent measurements. Only patients with measurable disease at baseline should be included. Measurable disease is defined by the presence of at least one measurable lesion (as detailed above).

